7.6. Body Weight

Body weight at each visit and change from baseline in body weight will be summarized using descriptive statistics (sample size, mean, SD, median, Q1, Q3, minimum, and maximum) by treatment group for each postbaseline analysis window, using subjects in the Safety Analysis Set

from baseline to Week 96. In the case of multiple values in an analysis window, data will be selected for analysis as described in Section 3.6.2.

This summary will be repeated for subjects in the Open-Label Safety Analysis Set from open-label baseline to Week 96.

7.7. Concomitant Medications

Concomitant medications (ie, medications other than study drug that are taken while receiving study drug) will be coded using the WHO Drug Dictionary. Use of concomitant medications for the open-label phase will be summarized (number and percentage of subjects) by treatment group and preferred name. Multiple drug use (by preferred name) will be counted only once per subject. The summary will be sorted by decreasing total frequency.

If the start or stop date of concomitant medications is incomplete, the month and year (or year alone if month is not recorded) of start or stop date will be used to determine if the medications are concomitant as follows. The medication is concomitant for the double-blind phase if the month and year of start or stop (or year of the start or stop) of the medication do not meet any of following criteria:

- The month and year of start of the medication is after the date of the last dose of blinded study drug
- The month and year of stop of the medication is before the date of the first dose of blinded study drug

The medication is concomitant for the open-label phase if the month and year of start or stop (or year of the start or stop) of the medication do not meet any of following criteria:

- The month and year of start of the medication is after the date of the last dose of open-label study drug
- The month and year of stop of the medication is before the date of the first dose of open-label study drug

If both the start and stop date of the medication are missing, the medication will be considered as concomitant during both double-blind and open-label phases.

If the start and stop date of the medications are not missing, and the start date is not after the last dose date of the blinded study drug and the stop date is not before the first dose date of the blinded study drug, or the medications are marked as ongoing and start date is on or before the last dose date of the blinded study drug, the medications are considered concomitant during the double-blind phase.

Similarly, if the start and stop date of the medications are not missing, and the start date is not after the last dose date of the open-label study drug and the stop date is not before the first dose date of the open-label study drug, or the medications are marked as ongoing and start date is on

or before the last dose date of the open-label study drug, the medications are considered concomitant during the open-label phase.

Summaries of concomitant medications will be provided for the open-label phase using the Safety Analysis Set. No inferential statistics will be provided. Subjects with any concomitant medication use will also be listed.

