1.2.4. Study Periods and Phases

The duration of double-blind treatment is 48 weeks. All subjects who complete 48 weeks of treatment are eligible for participation in the open label TAF 25-mg extension period for an additional 48 weeks (through Week 96). During the double-blind period only, subjects with a confirmed eGFR $_{CG}$ < 50 ml/min, and > 20% decline in estimated glomerular filtration rate (eGFR $_{CysC}$) by CKD-EPI (cystatin C) compared to baseline during the study, were required to undergo dose modification to every other day dosing of study drug. Subjects with confirmed creatinine clearance < 30 mL/min during the double-blind period of the study were to have the study drug discontinued.

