3.1.2. Safety Analysis Set

The Safety Analysis Set will include all randomized subjects who have received at least 1 dose of study drug. Subjects will be analyzed according to the treatment they actually received during the double-blind phase. The actual treatment received will differ from the randomized treatment only when their actual treatment differs from randomized treatment for the entire treatment duration during the double-blind phase. This is the primary analysis set for safety analyses.

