3.1.3. Open-Label Safety Analysis Set

The Open-Label Safety Analysis Set includes all randomized subjects who have received at least 1 dose of open-label study drug. Subjects will be analyzed according to the treatment they actually received during the double-blind phase.

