3.6. Analysis Visit Windows

3.6.1. Definition of Study Day 1 and Other Definitions

Study Day 1 is defined as the day when the first dose of blinded study drug was taken, as recorded on the Study Drug Administration eCRF.

Open-Label Study Day 1 is defined as the day when the first dose of the open-label study drug was taken, as recorded on the Study Drug Administration eCRF.

Study days are calculated relative to Study Day 1. For events that occurred on or after Study Day 1 date, study days are calculated as (visit date Study Day 1 + 1). For events that occurred prior to Study Day 1, study days are calculated as (visit date Study Day 1).

Open-Label Study days are calculated relative to Open-Label Study Day 1. For events that occurred on or after Open-Label Study Day 1, study days are calculated as (visit date Open-Label Study Day 1+1).

Follow-up days are for visits occurred during the treatment-free follow-up period and calculated as (visit date last dose date).

Last Dose Date of Blinded Study Drug is the latest non-missing end date of blinded study drug, recorded on the Study Drug Administration eCRF form with "Study Drug Permanently Withdrawn" box checked for subjects who prematurely discontinued blinded study drug or who completed blinded study drug according to the Blinded Study Drug Completion eCRF. If the last dose date of blinded study drug is missing (eg, due to lost to follow up) for subjects who prematurely discontinued blinded study drug or completed blinded study drug, or for subjects who are still on blinded study drug, the latest of non-missing blinded study drug start dates and end dates, the clinical visit dates, and the laboratory visit dates, excluding the dates during openlabel treatment and 24-week treatment-free follow up, will be used to impute the last dose date of blinded study drug.

For subjects who prematurely discontinued blinded study drug or who completed blinded study drug but did not enter the open-label phase, the **Last Dose Date** is the same as Last Dose Date of Blinded Study Drug.

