4.2.3. Duration of Exposure to Open-Label Study Drug

Duration of exposure to open-label study drug will be defined as (last dose date of open-label study drug first dose date of open-label study drug + 1), regardless of temporary interruptions in study drug administration, and will be expressed in weeks (recorded to 1 decimal place, eg, 4.5 weeks).

Duration of exposure to open-label study drug will be summarized using descriptive statistics (sample size, mean, SD, median, Q1, Q3, minimum, and maximum) and as the number and percentage of subjects exposed for specified periods, eg, \geq 12 weeks (84 days), \geq 24 weeks (168 days), \geq 36 weeks (252 days), \geq 48 weeks (336 days).

Summaries will be provided by treatment group for subjects in the Open-Label Safety Analysis Set. No inferential statistics will be provided.

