Adherence for open-label study drug will be calculated using all data from the entire open-label dosing period up to the date of permanent discontinuation of the open-label study drug for subjects who prematurely discontinued open-label study drug, or completed open-label study drug.

The number and percentage of subjects who return at least 1 bottle and have calculable adherence during the study, descriptive statistics for adherence for the open-label study drug regimen (sample size, mean, SD, median, Q1, Q3, minimum, and maximum) along with the number and percentage of subjects belonging to adherence categories (eg, < 80%, $\ge 80\%$ to < 90%, $\ge 90\%$ to < 95%, $\ge 95\%$) will be provided by treatment group for the Safety Analysis Set. No inferential statistics will be provided.

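### Open-label concomitant medication and adherence are summarised on the Safety Analysis Set, so the percentages of subjects rest on a denominator that includes people never dosed open-label

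*SAP*

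**What the plan says.** SAP Section 7.7 first describes the statistic: "Use of concomitant medications for the open-label phase will be summarized (number and percentage of subjects) by treatment group and preferred name". Its last paragraph then names the population: "Summaries of concomitant medications will be provided for the open-label phase using the Safety Analysis Set".

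SAP Section 4.2.4 covers adherence to open-label drug. It lists the number and percentage of subjects who returned a bottle and have calculable adherence, descriptive statistics for adherence, and the number and percentage in each adherence category. These "will be provided by treatment group for the Safety Analysis Set".

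The two candidate sets are defined a few pages earlier:

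- Section 3.1.2: "The Safety Analysis Set will include all randomized subjects who have received at least 1 dose of study drug". No open-label dose is required.
- Section 3.1.3: "The Open-Label Safety Analysis Set includes all randomized subjects who have received at least 1 dose of open-label study drug".

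The subsection immediately before the adherence text, Section 4.2.3 on open-label exposure, uses the second set: "Summaries will be provided by treatment group for subjects in the Open-Label Safety Analysis Set". So do the open-label summaries of adverse events (7.1.7), laboratory abnormalities (7.2.2.3), fractures (7.3.3), bone events (7.3.5) and dipstick proteinuria (7.4.4).

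**The concern.** The two sets differ by design. Section 1.2.4 ties open-label entry to finishing the blinded phase: "All subjects who complete 48 weeks of treatment are eligible for participation in the open label TAF 25-mg extension period". Section 3.6.1 provides for subjects who stop blinded drug early and for those "who completed blinded study drug but did not enter the open-label phase". Both groups belong to the Safety Analysis Set and have no open-label drug, bottle or treatment period.

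In these two summaries such subjects would count in the denominator but could not normally reach the numerator. Section 7.7 itself describes concomitant medication as medication taken while on study drug, which a subject without an open-label dose cannot satisfy for that phase. The reported percentages would be too low, and they would rest on a different N from the open-label exposure and adverse event tables beside them.

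**Working it through.** **Plan figure.** The documents state no expected percentage for either summary, so there is none to reproduce. The planned 230 per arm (SAP Section 1.3) serves only as an illustrative denominator. It does reproduce: with a 2.4% rate in both arms, a 4% margin and one-sided 0.025, the unpooled normal approximation gives 230 per arm for 80% power, and the power at 230 is 80.0%.

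**Formula.** Let d be the share of the Safety Analysis Set that never takes open-label drug. Then

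percentage on Safety Analysis Set = percentage on Open-Label Safety Analysis Set × (1 − d).

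**Input for d.** It is not given for this trial. I assume 2% to 10%. Within that range 4.9% is a reference point: in the two earlier Phase 3 studies, 63 of 1298 treated subjects discontinued blinded drug (Protocol Section 1.2.3, Overall Extent of Exposure). The 60% and 30% levels of use are also illustrative.

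| d (assumed) | Multiplier | True 60% appears as | True 30% appears as | Ceiling for calculable adherence |
|---|---|---|---|---|
| 2% | 0.980 | 58.8% | 29.4% | 98.0% |
| 4.9% | 0.951 | 57.1% | 28.5% | 95.1% |
| 10% | 0.900 | 54.0% | 27.0% | 90.0% |

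**In whole subjects.** With 230 in an arm and d = 4.9%, 219 enter. Then 131 users are 131/219 = 59.8% of the open-label set and 131/230 = 57.0% of the Safety Analysis Set, a gap of 2.9 points. If all 219 have calculable adherence, the table shows 219/230 = 95.2% instead of 100%.

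**Which statistics are affected.**

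- Percentage of subjects using each medication: diluted.
- Percentage with calculable adherence: diluted.
- Mean, SD, median, quartiles and range of adherence: unaffected. Section 4.2.4 computes adherence from tablets dispensed and returned, so a subject never given open-label drug has no value to contribute.
- Adherence categories: the denominator is not stated. They are diluted if it is the named set, and unaffected if it is subjects with calculable adherence.

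**An effect in the other direction.** Under Section 7.7, a medication with both dates missing counts as concomitant in both phases. On the Safety Analysis Set this could put a subject never dosed open-label into the numerator. Partial dates may do the same, because the exclusion rules refer to open-label dose dates that such a subject lacks.

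**The case against.** The strongest reply is that this is a wording slip with little consequence, and much of that stands. Section 3.1 requires every table to show its analysis set in the subtitle and reports the size of each set by arm. Section 4.1 also reports the number in the Open-Label Safety Analysis Set. Since counts accompany the percentages, a reader can rebase any medication figure by one division. Both sections rule out inferential statistics, and neither summary is an endpoint.

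A second reply is that Section 4.1 also places open-label drug completion on the Safety Analysis Set, so the usage is not confined to these two places. That is a disposition table, which follows all treated subjects and includes whether they were willing to enter the open-label phase. The wider denominator has a purpose there that it lacks for medication use or adherence within the phase. The introduction to Section 7 assigns cumulative open-label safety data to the Open-Label Safety Analysis Set, which supports reading 7.7 as a slip.

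Two stronger readings need to be set aside. A reader might infer that open-label adherence as a whole is understated. The documents do not support that, because the mean, median and quartiles use only subjects with a calculable value.

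A reader might also infer that the arms are diluted unequally and that a spurious treatment difference would appear. Unequal entry would have that effect, but nothing in the documents points to it. The earlier studies show almost equal blinded-drug discontinuation: 4.8% on TAF and 4.9% on TDF. At those rates an equal 60% use would appear as 60 × 0.952 = 57.12% and 60 × 0.951 = 57.06%, a gap of 0.06 points. Those rates also come from a different population and measure discontinuation up to a data cut, not failure to enter an extension, so they are only a rough guide.

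**Conclusion.** The point holds as a minor denominator error. Followed as written, Sections 7.7 and 4.2.4 give percentages of subjects for open-label medication use and for calculable adherence on a set that is too large. Across an assumed non-entry of 2% to 10%, the understatement at a true 60% is about 1.2 to 6.0 points. It is smaller for less common medications and zero if every treated subject entered the open-label phase.

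Understatement is the likely net direction but not certain for every medication, because the missing-date rule can add a few numerator counts. Whether the adherence categories are affected cannot be settled from the text. No primary, key secondary or other inferential result depends on either summary.

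**What to change.** In Section 4.2.4 and in the last paragraph of Section 7.7, replace Safety Analysis Set with Open-Label Safety Analysis Set, as Section 4.2.3 already does. In 4.2.4, add that the adherence-category percentages use subjects with calculable open-label adherence. The change of set also keeps subjects never dosed open-label from being counted through the missing-date rule.

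The cost is two set names and one sentence, with no new data and no new analysis. If the SAP is already final, Section 1 requires later changes to be documented in the CSR, so a short entry there is also needed.

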7.8. Electrocardiogram (ECG) Results

The number and percentage of subjects with an investigator's ECG assessment of normal, abnormal but not clinically significant, or abnormal and clinically significant will be summarized by treatment group for subjects in the Safety Analysis Set from baseline to Week 96. This summary will be repeated for subjects in the Open-Label Safety Analysis Set from open-label baseline to Week 96. No inferential statistics will be provided.

A by-subject listing of safety ECG results will be provided including treatment, assessment date and time, and ECG results.

7.9. Other Safety Measures

A data listing will be provided for subjects experiencing pregnancy during the study.

Listings of cirrhosis and hepatocellular carcinoma assessment results will be provided.

7.10. Changes From Protocol-Specified Safety Analyses

There are no deviations from the protocol-specified safety analyses.

8. PATIENT REPORTED OUTCOMES

The effect of treatment on health related quality of life questionnaires (via SF-36, CLDQ, and WPAI questionnaires) will be analyzed by visit for subjects in the Safety Analysis Set for the entire study treatment period (ie, from baseline up to Week 96), and separately for subjects in the Open-Label Safety Analysis Set for the open-label phase only (ie, from open-label baseline up to Week 96).

8.1. Definition of Patient Reported Outcomes

8.1.1. SF-36

The Short Form-36 (SF-36) includes 11 questions with multiple sub-questions that yield a total of 36 questions. The responses are rated on a 3-point, 5-point, or 6-point scale, and scoring are performed on 8 domains: Physical function (PF), Role physical (RP), Bodily Pain (BP), General health perceptions (GH), Vitality (VT), Social functioning (SF), Role emotional (RE), Mental health (MH).

Scale	Item	Abbreviated Item Content					
	3a	Vigorous activities, such as running, lifting heavy objects, or participating in strenuous sports					
	3b	Moderate activities, such as moving a table, pushing a vacuum cleaner, bowling, or playing golf					
	3c	Lifting or carrying groceries					
	3d	Climbing several flights of stairs					
Physical Functioning (PF)	3e	Climbing one flight of stairs					
	3f	Bending, kneeling, or stooping					
	3g	Walking more than a mile					
	3h	Walking several hundred yards					
	3i	Walking one hundred yards					
	3j	Bathing or dressing oneself					
	4a	Cut down the amount of time one spent on work or other activities					
	4b	Accomplished less than you would like					
Role-Physical (RP)	4c	Limited in kind of work or other activities					
	4d	Had difficulty performing work or other activities (e.g., it took extra effort)					
Podity Pain (PD)	7	Intensity of bodily pain					
Bodily Pain (BP)	8	Extent pain interfered with normal work					

Scale	Item	Abbreviated Item Content
	1	Is your health: excellent, very good, good, fair, poor
	11a	Seem to get sick a little easier than other people
General Health (GH)	11b	As healthy as anybody I know
	11c	Expect my health to get worse
	11d	Health is excellent
	9a	Feel full of life
V:4-1:4 (V/T)	9e	Have a lot of energy
Vitality (VT)	9g	Feel worn out
	9i	Feel tired
Social Experience (SE)	6	Extent health problems interfered with normal social activities
Social Functioning (SF)	10	Frequency health problems interfered with social activities
	5a	Cut down the amount of time spent on work or other activities
Role-Emotional (RE)	5b	Accomplished less than you would like
	5c	Did work or other activities less carefully than usual
	9b	Been very nervous
	9c	Felt so down in the dumps that nothing could cheer you up
Mental Health (MH)	9d	Felt calm and peaceful
	9f	Felt downhearted and depressed
	9h	Been happy
Health Transition (HT)	2	How health is now compared to before

Two summary scales will be presented based on the domain scores:

- Physical component summary (PCS): combines PF, RP, BP, and GH
- Mental component summary (MCS): combines VT, SF, RE, and MH

The summary scores aggregate information from the 8 SF-36 domains in a way that captures 80% to 85% of the variance in the 8 domains.

The SF-36 physical component and the mental component scores will be calculated based on the 8 domain scores using the SF-36v2 scoring method (http://www.sf-36.org/demos/SF-36v2.html).

8.1.2. CLDQ

The Chronic Liver Disease Questionnaire (CLDQ) includes 29 questions which aim to survey how subjects felt during the last two weeks. The responses are rated on a 7-point scale, and

translated into 6 domain scores: fatigue, activity, emotional function, abdominal symptoms, systemic symptoms, and worry, and an overall CLDQ score. Specifically,

- Abdominal symptoms (AB) Mean of {R1, R5, R17}
- Fatigue (FA) Mean of {R2, R4, R8, R11, R13}
- Systemic (SY) Mean of {R3, R6, R21, R23, R27}
- Activity (AC) Mean of {R7, R9, R14}
- Emotion (EM) Mean of {R10, R12, R15, R16, R19, R20, R24, R26}
- Worry (WO) Mean of {R18, R22, R25, R28, R29}

where R# is the response to question number # (eg, R1 is the response to question 1).

The overall CLDQ score will then be calculated by taking the mean of 6 domain scores.

8.1.3. WPAI:SHP

The Work Productivity and Activity Impairment Questionnaire: Specific Health Hepatitis (WPAI:SHP) includes 6 questions that are summarized into a four WPAI:SHP scores. The first question is to determine the employment status. Questions 2 through 5 are applicable to employed patients only. Using subject responses to six questions, four scores are derived:

- percentage of absenteeism,
- percentage of presenteeism (reduced productivity while at work),
- an overall work impairment score that combines absenteeism and presenteeism and
- percentage of impairment in activities performed outside of work.

Greater scores indicate greater impairment (http://www.reillyassociates.net/WPAI Scoring.html).

Score	Source	Formula
Absenteeism	Question 2: During the past seven days, how many hours did you miss from work because of {your health problems}?	100 x [Q2/(Q2+Q4)]
	Question 4: During the past seven days, how many hours did you actually work?	
Presenteesism	Question 5: During the past seven days, how much did {your health problems} affect your productivity while you were working?	100 x [(Q5)/10]
Work Productivity Loss	Question 2: During the past seven days, how many hours did you miss from work because of {your health problems}?	100 x [Q2/(Q2+Q4) + {1 - Q2/(Q2+Q4)}x(Q5)/10]
	Question 4: During the past seven days, how many hours did you actually work?	
	Question 5: During the past seven days, how much did {your health problems} affect your productivity while you were working?	
Activity Impairment	Question 6: During the past seven days, how much did {your health problems} affect your ability to do your regular daily activities, other than work at a job?	100 x [(Q6)/10]

For the WPAI:SHP, four scores will be calculated based on the results.

8.2. Analysis Methods for Patient Reported Outcomes

Descriptive statistics for each of the SF-36 domains, and physical and component scores, CLDQ domain and overall scores, and the WPAI:SHP scores at baseline, Week 24, Week 48, Week 96, and change from baseline at Week 24, Week 48, and Week 96, will be presented by treatment group for subjects in the Safety Analysis Set from baseline to Week 96. Change from baseline for each score will be compared between treatment groups using a 2-sided Wilcoxon rank-sum test.

This will be repeated for subjects in the Open-Label Safety Analysis Set from open-label baseline to Week 96, using open-label baseline in place of baseline, and no statistical comparisons will be performed.

A by-subject listing for the scores from each of the questionnaires will be provided by subject ID number and visits in chronological order.

